7.2 Adverse Event Reporting

All bleeding/thrombotic Adverse Events will be tracked by the research team using an adverse event log. All unanticipated adverse events and SAE's will be reported to the IRB. Annual summaries of adverse events will be reported to the IRB.

Adverse events will be graded according to CTCAE v4.03. Both Serious and Non-Serious Adverse Events will be clearly noted in source documentation and listed on study specific Case Report Forms (CRFs). The Protocol Director (PD) or designee will assess each Adverse Event (AE) to determine whether it is unexpected according to the Informed Consent, Protocol Document, or Investigator's Brochure, and related to the investigation. All Serious Adverse Events (SAEs) will be tracked until resolution, or until 30 after the last dose of the study treatment.

SAEs CTCAE Grade 3 and above, and all subsequent follow-up reports will be reported to the Stanford Cancer Institute Data and Safety Monitoring Committee (DSMC) using the study specific CRF regardless of the event's relatedness to the investigation. Following review by the DSMC, events meeting the IRB definition of 'Unanticipated Problem' will be reported to the IRB using eProtocol within 10 working days of DSMC review, or within 5 working days for deaths or life-threatening experiences.

8. STUDY CALENDAR

	Pre-Study	12 -16 hours post surgery ending at time of inpatient discharge	Time of hospital discharge	90 days post surgery
Investigational Agent ^{1,2}		X		
Informed consent	X			
Demographics	X			
Medical history	X			
Concurrent meds	X			
Physical exam	X	X		
Vital signs	X	X		
Height	X			
Weight	X			
Caprini Score	X			
CBC	X	X		
Serum chemistry	X	X		
Adverse event evaluation			X	X
90 Day Phone Call				X

1. Apixaban 2.5 mg PO BID starting 12-16 hours after completing skin closure.
2. Enoxaparin 40 mg SC QD starting 12-16 hours after completing skin closure

9. MEASUREMENTS

For clinicaltrials.gov and Stanford Clinical Trials Directory compliance

Primary Outcome Measure: The primary study outcome is defined as overall bleeding event risk 90 days post-randomization. Secondary patient-oriented outcomes include risk of VTE events

Title: A Randomized Controlled Trial Comparing Apixaban Versus Enoxaparin Following Microsurgical Breast Reconstruction

- **Time Frame:** 90 days post-randomization.
- **Safety Issue:** We are not measuring a safety issue.

9.1 Primary and Secondary Outcome measures

The primary study outcome is defined as overall bleeding event risk 90 days post-randomization. Secondary patient-oriented outcomes include risk of VTE events. Tertiary outcomes include: length of stay, location of patient on day 90 of follow up (home vs. SNF, etc), and clinically significant wound complications (infection, dehiscence, flap loss).

Process measures to be collected include time to starting anticoagulation after completion of skin closure, number of days patients received anticoagulation treatment, and timing of phone interview follow up.

Conservative estimates from recent retrospective study in over 1500 patients who underwent body contouring procedures (LMWH [N=454]; rivaroxaban [N=703], apixaban [N=415]) are used for our power analysis (37). Using standard formulas, with 80% power to detect a non-inferiority margin of -0.075, and assuming a 1.32% baseline in bleeding events among patients dosed on daily enoxaparin compared with a 1.73% rate of bleeding in direct oral anticoagulant (DOAC) arm patients over 90 days, our analysis expects enrollment size of 37 patients per arm. We conservatively estimate a 25% dropout rate over the course of the study, which results in a sample size of 100 (50 patients per arm).

The primary conclusions of this project will be analyzed based on intention-to-treat where all randomized patients will be analyzed within the groups they were originally allocated to. Two-sided 5% significance levels will be used to identify statistically significant results. Unadjusted analysis of the bleeding risk in apixaban use will be assessed using an exact Pearson chi-squared test. The outcome will be reported as an odds ratio with 95% confidence intervals. Baseline prognostic variables including age, BMI, Caprini score, Elixhauser comorbidity index score, procedure duration, unilateral vs. bilateral will be ascertained upon enrollment and reported by our study group. A subsequent covariate adjusted analysis will be undertaken with an adjusted logistic regression model.

10. REGULATORY CONSIDERATIONS

10.1 Institutional Review of Protocol

The protocol, the proposed informed consent and all forms of participant information related to the study (e.g. advertisements used to recruit participants) will be reviewed and approved by the Stanford IRB and Stanford Cancer Institute Scientific Review Committee (SRC). Any changes made to the protocol will be submitted as a modification and will be approved by the IRB prior to implementation. The Protocol Director will disseminate the protocol amendment information to all participating investigators.

10.2 Data and Safety Monitoring Plan

The Stanford Cancer Institute Data and Safety Monitoring Committee (DSMC) will be the monitoring entity for this study. The DSMC will audit study-related activities to determine whether the study has been conducted in accordance with the protocol, local standard operating procedures, FDA regulations, and Good Clinical Practice (GCP). This may include review of the following types of documents participating in the study: regulatory binders, case report forms, eligibility checklists, and source documents. In addition, the DSMC will regularly review serious

adverse events and protocol deviations associated with the research to ensure the protection of human subjects. Results of the DSMC audit will be communicated to the IRB and the appropriate regulatory authorities at the time of continuing review, or in an expedited fashion, as needed.

10.3 Data Management Plan

The Protocol Director, or his designee, will prepare and maintain adequate and accurate participant case histories with observations and data pertinent to the study. Report Forms (CRFs) will document treatment outcomes for data analysis. Case report forms will be developed using the REDCap database system and will be maintained by the protocol director. CRFs will be kept in a locked office, only accessible to the research team. Study specific Case

11. STATISTICAL CONSIDERATIONS

11.1 Statistical Design

The primary study outcome is defined as overall bleeding event risk 90 days post-randomization. Secondary patient-oriented outcomes include risk of VTE events. Tertiary outcomes include: length of stay, location of patient on day 90 of follow up (home vs. SNF, etc), and clinically significant wound complications (infection, dehiscence, flap loss).

Process measures to be collected include time to starting anticoagulation after completion of skin closure, number of days patients received anticoagulation treatment, and timing of phone interview follow up.

Conservative estimates from recent retrospective study in over 1500 patients who underwent body contouring procedures (LMWH [N=454]; rivaroxaban [N=703], apixaban [N=415]) are used for our power analysis (37). Using standard formulas, with 80% power to detect a non-inferiority margin of -0.075, and assuming a 1.32% baseline in bleeding events among patients dosed on daily enoxaparin compared with a 1.73% rate of bleeding in direct oral anticoagulant (DOAC) arm patients over 90 days, our analysis expects enrollment size of 37 patients per arm. We conservatively estimate a 25% dropout rate over the course of the study, which results in a sample size of 100 (50 patients per arm).

The primary conclusions of this project will be analyzed based on intention-to-treat where all randomized patients will be analyzed within the groups they were originally allocated to. Two-sided 5% significance levels will be used to identify statistically significant results. Unadjusted analysis of the bleeding risk in apixaban use will be assessed using an exact Pearson chi-squared test. The outcome will be reported as an odds ratio with 95% confidence intervals. Baseline prognostic variables including age, BMI, Caprini score, Elixhauser comorbidity index score, procedure duration, unilateral vs. bilateral will be ascertained upon enrollment and reported by our study group. A subsequent covariate adjusted analysis will be undertaken with an adjusted logistic regression model.

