7. ADVERSE EVENTS AND REPORTING PROCEDURES

7.1 Potential Adverse Events

The primary safety outcome is bleeding during the treatment period or until 2 days after the last dose of the study medication was administered (Lassen et al. NEJM 2020;26:2487-2498). Bleeding is categorized as major, clinically relevant nonmajor, or minor bleeding and as the composite of major and clinically relevant nonmajor bleeding. The definition of major bleeding is acute, clinically overt bleeding accompanied by one or more of the following findings: a decrease in the hemoglobin level of 2 g per deciliter or more over a 24-hour period; transfusion of 2 or more units of packed red cells; bleeding at a critical site (including intracranial, intraspinal, intraocular, pericardial, and retroperitoneal bleeding); bleeding into the operated joint, necessitating reoperation or intervention; intramuscular bleeding with the compartment syndrome; or fatal bleeding. Clinically relevant nonmajor bleeding includes acute, clinically overt episodes such as wound hematoma, bruising or ecchymosis, gastrointestinal bleeding, hemoptysis, hematuria, or epistaxis that does not meet the criteria for major bleeding. Bleeding is categorized as minor if it is clinically overt but is not adjudicated as major or clinically relevant nonmajor bleeding.

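### The planning bleeding rates are called conservative, but with a fixed 7.5-point margin low rates are the favourable input, and no power is shown for higher rates

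*Combined protocol and SAP*

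**What the plan says.** Section 11.1 takes its planning rates from "Conservative estimates from recent retrospective study in over 1500 patients who underwent body contouring procedures". The power claim is worded "with 80% power to detect a non-inferiority margin of -0.075". The control arm enters the calculation by "assuming a 1.32% baseline in bleeding events among patients dosed on daily enoxaparin"; for the apixaban arm the plan uses 1.73%, also to day 90. The result is stated as follows: "our analysis expects enrollment size of 37 patients per arm". A 25% dropout allowance then gives 50 per arm and 100 in total. The same text stands in sections 9.1 and 11.4.

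The significance level appears in the next paragraph: "Two-sided 5% significance levels will be used to identify statistically significant results". The power sentence itself names no level.

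The primary outcome is overall bleeding to 90 days. Section 7.1 divides bleeding into major, clinically relevant nonmajor and minor, and the middle category is wide: "Clinically relevant nonmajor bleeding includes acute, clinically overt episodes such as wound hematoma, bruising or ecchymosis". The trial population has free abdominal flap breast reconstruction; the source cohort had body contouring. No section explains why the rates are conservative or shows size or power at any other rate.

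**The concern.** A planning input is conservative if an error in the likely direction leaves the trial with at least the power claimed. For non-inferiority on a risk difference with a fixed margin, the variance term p(1−p) grows with p over the whole plausible range. A low assumed rate therefore gives a small trial, and a higher true rate costs power. The label describes the opposite of how the calculation behaves.

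What is at stake is how the power claim and a missed margin are read. A committee may take the word to mean that the size has slack against a wrong rate. If bleeding is more common than 1.32%, the chance of missing the margin rises even when apixaban is no worse than assumed, and such a miss could be mistaken for evidence of harm.

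**Working it through.** **Inputs (section 11.1).** Enoxaparin rate p0 = 0.0132; apixaban rate p1 = 0.0173; difference 0.0041; margin 0.075, read as the largest acceptable absolute excess; power 80%; 37 evaluable and 50 randomised per arm; two-sided 5% level, which is one-sided 2.5% for non-inferiority.

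**Reproducing the plan's figure.** Unpooled normal approximation:

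n per arm = (z_α + z_0.80)² × [p0(1−p0) + p1(1−p1)] / (0.075 − (p1 − p0))²

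- Variance sum: 0.0132 × 0.9868 + 0.0173 × 0.9827 = 0.03003.
- Denominator: 0.0709² = 0.005027.
- One-sided 5%: (1.645 + 0.8416)² = 6.183, so n = 6.183 × 0.03003 / 0.005027 = 36.9, which rounds up to 37. This matches. Then 37/0.75 = 49.3, rounded up to 50 per arm.
- One-sided 2.5%: (1.960 + 0.8416)² = 7.849, so n = 46.9, which rounds up to 47.

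The printed 37 therefore corresponds to a one-sided 5% level that the documents never state.

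**Where 1.32% comes from.** 6/454 = 1.32%, and 454 is the size of the source's low molecular weight heparin group. The rate thus appears to be that group's raw proportion. If so, its exact 95% confidence interval is about 0.5% to 2.9%, so the planning value is the centre of the interval, not an upper value.

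**Does the assumed excess on apixaban compensate?** With equal rates the formula becomes n = (z_α + z_0.80)² × 2p(1−p) / 0.075². At one-sided 5%:
- Equal 1.32%: 28.6, so 29 per arm. Assuming a 0.41-point excess therefore costs 8 per arm (37 − 29), a mildly cautious choice.
- Equal 2%: 6.183 × 0.0392 / 0.005625 = 43.1, so 44 per arm. A rise to 2% with no excess at all already needs more than 37.

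**Power over a range of baselines.** Keep the 0.41-point difference: Power = Φ[0.0709/SE − z_α], with SE = √{[p0(1−p0) + p1(1−p1)]/n} and p1 = p0 + 0.0041. For example, at p0 = 3% and n = 37 the variance sum is 0.06204, SE = 0.04095 and 0.0709/SE = 1.731. Power is Φ(1.731 − 1.960) = 41.0% at one-sided 2.5% and Φ(1.731 − 1.645) = 53.5% at one-sided 5%.

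| Enoxaparin rate | 37 per arm, one-sided 2.5% | 50 per arm, one-sided 2.5% | 37 per arm, one-sided 5% |
|---|---|---|---|
| 1.32% (plan) | 70.2% | 82.5% | 80.1% |
| 2% (assumed) | 54.7% | 67.5% | 66.7% |
| 3% (assumed) | 41.0% | 52.1% | 53.5% |
| 5% (assumed) | 27.9% | 35.8% | 39.3% |
| 10% (assumed) | 17.0% | 21.5% | 26.2% |

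The 50-per-arm column assumes no dropout. About 2.9%, the upper limit of the source's apparent interval, lies close to the 3% row.

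**Limit of the method.** At 37 per arm the expected events are 37 × 0.0132 = 0.49 and 37 × 0.0173 = 0.64, so the normal approximation is rough. It is used here because it reproduces the plan's figure; the table shows direction and approximate size.

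**The case against.** The strongest defence is that conservative may mean something else: the higher of several rates in the cited study, or the allowance for slightly more bleeding on apixaban. The cited study is not available here, so the first reading cannot be excluded. The second is partly right, but equal rates of 2% already outweigh it. Either reading would need a justification, and none is printed.

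The plan also makes its power conditional on the assumed rates, so it does not claim power regardless of them. That stands, and it is why the remedy is a matter of wording and display. The other cautious statement, "We conservatively estimate a 25% dropout rate over the course of the study", concerns retention and is not an allowance for a higher bleeding rate: with nobody lost, power at a 5% baseline is still only about 36% at the stated level.

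A reader might infer more than the documents support:

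- **That the true rate is higher than 1.32%.** The wide definition in section 7.1 and the different surgery make this plausible, but no rate is given for this population and endpoint. Section 7.1 also ends its bleeding window two days after the last dose, whereas section 11.1 uses 90 days. After discharge, capture rests on patient reports and one call at day 90. Fuller capture than in the source is therefore not established.
- **That the stated power is a best case, or holds only at 1.32% v 1.73%.** Neither is so. At one-sided 5%, equal rates of 1.32% give 88% power at 37 per arm, and equal rates of 2% give 85% at 50. Lower rates or full retention also raise power.
- **That a modest rise makes failure probable.** At one-sided 5%, power at a 3% baseline is still slightly above one half with 37 per arm and 64% with 50.
- **That any missed margin at higher rates is merely inconclusive.** With 15/50 v 5/50 the difference is 20 points (Newcombe 95% interval 4 to 35). That misses the margin and also shows excess bleeding.

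**Conclusion.** The point holds in this form: the label is unsupported and runs opposite to the way the calculation behaves, and the plan shows no sensitivity to the bleeding rate. The direction follows from the formula alone and needs no outside rate. The size depends on assumed baselines. At the stated two-sided 5% level with 37 evaluable per arm, power runs from 70% at the planned rates to 41% at 3% and 17% at 10%.

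These figures rest on the unpooled normal approximation, a constant 0.41-point difference, and the margin read as an absolute excess of 7.5 points. The link from 1.32% to 6/454 is an inference from matching arithmetic. The documents do not show that the planning rates are too low, only that nothing supports calling them conservative.

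**What to change.** In sections 9.1, 11.1 and 11.4:

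1. Delete the word conservative where it describes the source rates.
2. State that the power is conditional on 1.32% v 1.73%, and that the documents have no bleeding rate for this population and endpoint.
3. Print the power range at the stated two-sided 5% level (one-sided 2.5%) for 37 and 50 per arm, as in the first two power columns of the table, with baselines above 1.32% marked as assumptions. If one-sided 5% is intended, say so and print the column for that level.
4. Add a reporting rule. A result is inconclusive only when the confidence interval for the risk difference (apixaban minus enoxaparin) includes both zero and the 7.5-point margin. An interval wholly above zero is reported as excess bleeding. This requires an interval for the risk difference, since the plan currently names only an odds ratio.

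The cost is protocol wording and one additional reported interval. No patients are added. The downside is that the stated power becomes less favourable.

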2.3 Rationale

Venous thromboembolism (VTE) continues to be a major patient safety issue after surgical intervention. Significant morbidity and mortality are associated with the development of VTE. With over 100,000 annual VTE-related deaths in the U.S., this disease entity represents the most common cause of preventable in-hospital death (10, 11). Furthermore, the associated economic burden is substantial, with annual costs to the U.S. healthcare system in excess of \$7 billion (12).

The importance of VTE prevention has been recognized by organized plastic surgery. Significant resources have been

invested into raising awareness and improving VTE risk stratification and prophylaxis in patients undergoing plastic and reconstructive surgery. Initiatives such as the American Society of Plastic Surgeons (ASPS) VTE Task Force, the Plastic Surgery Foundation (PSF)-funded VTE Prevention Study (VTEPS) as well as initiatives by the American Association of Plastic Surgeons (AAPS) reflect the significant emphasis placed on this particular area of clinical research (3, 11, 13, 14). Important questions, however, remain unanswered and include issues such as appropriate dosing as well as duration of VTE chemoprophylaxis. Furthermore, mechanisms underlying 'breakthrough' VTE events, defined as VTE events despite guideline-compliant chemoprophylaxis, remain unknown. VTEPS demonstrated that despite daily enoxaparin prophylaxis 1 patient in 25 with a Caprini score >8 had a breakthrough VTE event (3). The occurrence of breakthrough VTE events highlights the need for an improved approach to VTE chemoprophylaxis.

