VTE risk stratification and clinical research in other specialties have identified cancer patients as a particularly vulnerable patient population (15, 16). Of these, breast cancer patients represent the largest group treated by plastic surgeons. Symptomatic VTE has been reported in up to 4% of patients undergoing autologous reconstruction using abdominal flaps (17). An up to 20% rate of asymptomatic VTE after autologous reconstruction has been reported (18). In light of rising numbers of breast reconstruction in the U.S., with more than 18,000 autologous reconstructions in 2013, a 35% increase in the number of annual breast reconstructions since 2000, and over 106,000 breast reconstructions in 2015 alone, the number of patients at risk for VTE is alarmingly high (19-21). It is important to note that an increased rate of DVT formation has been reported following autologous vs. implant-based breast reconstruction despite guideline-compliant prophylaxis (22). These findings are particularly relevant in light of an increasing number of patients undergoing prophylactic bilateral mastectomy with immediate reconstruction. As such, it is of no surprise that the ASPS VTE Task Force identified "major breast reconstruction" as a procedure warranting additional prophylactic considerations (11). Given the large number of patients at risk, particular emphasis on understanding the processes leading to VTE development in this patient population is warranted. A recent retrospective study in over 1500 patients who underwent body contouring procedures (LMWH [N=454]; rivaroxaban [N=703], apixaban [N=415]) demonstrated similar rates of bleeding-related adverse events (37).

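### The trial is sized on an unexplained 7.5-point bleeding margin (8.82% against an assumed 1.32%) that the planned analysis never tests, so meeting it could not support a claim of similar bleeding

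*Combined protocol and SAP*

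**What the plan says.** Sections 9.1, 11.1 and 11.4 carry the same sample-size text. The primary outcome is overall bleeding by 90 days after randomization. The calculation is made "with 80% power to detect a non-inferiority margin of -0.075, and assuming a 1.32% baseline in bleeding events among patients dosed on daily enoxaparin". The assumption for the apixaban arm is worded as "compared with a 1.73% rate of bleeding in direct oral anticoagulant (DOAC) arm patients over 90 days". From these inputs the plan concludes that "our analysis expects enrollment size of 37 patients per arm". A 25% dropout allowance brings this to 50 per arm, 100 in total. Both rates come from a retrospective study of body-contouring patients.

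On analysis, the same sections state that "Two-sided 5% significance levels will be used to identify statistically significant results". They name an exact Pearson chi-squared test, an odds ratio with 95% confidence limits, and a later adjusted logistic regression. They name no non-inferiority test and no rule for comparing a result with the margin.

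Section 7.1 grades bleeding as major, clinically relevant nonmajor (bruising and ecchymosis included) or minor. I read overall bleeding in 9.1 and 11.1 as all of these. No section explains why 7.5 points was chosen.

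**The concern.** A non-inferiority margin states how much extra harm would still be accepted. Here it is several times the event rate assumed on the comparator, and it applies to a single outcome that mixes major bleeding with bruising. Bleeding is the primary objective, and Section 2.3 introduces the retrospective study as having found similar bleeding rates. A result reported as non-inferior would readily be taken to confirm that similarity, and nothing in the plan prevents it.

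The second half of the problem is that sizing and analysis do not meet. The trial is sized on a risk difference against a margin, but the planned analysis tests equality and reports an odds ratio. As written, the trial could finish without stating the one quantity it was sized to estimate.

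**Working it through.** **Inputs (Section 11.1).** Enoxaparin 0.0132; apixaban 0.0173; expected difference 0.0041; margin 0.075; power 80%; 37 per arm evaluable, 50 randomized.

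**1. Reproducing 37.** Unpooled normal formula:

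n = [p_E(1−p_E) + p_A(1−p_A)] × (z_α + z_β)² / (margin − difference)²

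The variance sum is 0.0132×0.9868 + 0.0173×0.9827 = 0.03003. The denominator is (0.075 − 0.0041)² = 0.005027.

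- One-sided 5%: 0.03003 × 6.183 / 0.005027 = 36.93, so 37, as stated.
- One-sided 2.5%: 0.03003 × 7.849 / 0.005027 = 46.88, so 47.

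The margin is therefore an absolute difference of 7.5 points, despite the minus sign. The mismatch between one-sided 5% and the stated two-sided 5% level is a separate matter.

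**2. What the margin accepts.**

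- Boundary: 1.32% + 7.5 points = 8.82%.
- Ratio of rates: 8.82 / 1.32 = 6.7.
- Odds ratio: (0.0882/0.9118) / (0.0132/0.9868) = 7.2.
- The excess alone: 7.5 / 1.32 = 5.7 times the control rate, and 7.5 / 0.41 = 18 times the expected difference.

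**3. Dependence on the baseline.** The rows below the first are assumptions; the documents give no rate for free-flap patients.

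| Enoxaparin rate | Boundary | Ratio |
|---|---|---|
| 1.32% (plan) | 8.82% | 6.7 |
| 3% | 10.5% | 3.5 |
| 5% | 12.5% | 2.5 |
| 10% | 17.5% | 1.75 |

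**4. What the size can exclude.** Expected bleeds at 50 per arm are 50×0.0132 = 0.66 and 50×0.0173 = 0.87. The chance of no bleed in either arm is (0.9868×0.9827)^50 = 21.5%, and the odds ratio is then undefined. With no events, the Newcombe 95% upper limit for the difference reduces to z²/(n+z²):

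- 50 per arm: 3.84 / 53.84 = 7.1 points.
- 37 per arm: 3.84 / 40.84 = 9.4 points.

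**5. How often a higher-bleeding drug would meet the margin.** The plan gives no rule, so I assumed one: the margin is met when the upper limit for the difference is below 7.5 points. I summed binomial probabilities over all outcomes at 50 per arm, with enoxaparin at 1.32%.

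| True apixaban rate | Upper limit used | Margin met |
|---|---|---|
| 3.96% (tripled) | Newcombe, two-sided 95% | 17% |
| 3.96% (tripled) | Wald, two-sided 95% | 41% |
| 3.96% (tripled) | Wald, one-sided 5% | 45% |
| 1.73% (as planned) | Newcombe, two-sided 95% | 47% |

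At 37 per arm the Newcombe figures are 9% (tripled) and 21% (as planned).

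**6. The planned analysis against the margin.** The chi-squared test asks whether the two rates are equal. Failing to reject equality is not evidence that the difference is below 7.5 points. An odds-ratio interval can be compared with the margin only by fixing a baseline: 7.2 is the equivalent at 1.32% and at no other rate.

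**The case against.** The strongest reply is that the protocol never promises the conclusion at issue. Its objective is to examine bleeding rates, it sets no non-inferiority rule, and an odds ratio with 95% limits would show how imprecise the result is. That is a fair reading of the text and lowers the severity. It does not remove the point: the stated power refers to a non-inferiority question, and nothing says how the answer will be worded.

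It can also be said that 1.32% is too low for free-flap surgery under the broad bleeding definition in 7.1, so the true multiple would be smaller. That stands, and is why the multiple is given as a range. It does not rescue the sample size, because 1.32% is the rate on which the 80% power was calculated.

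Four stronger readings are tempting but unsupported.

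- A reader might infer that the accepted excess is larger than all the symptomatic VTE that prophylaxis could prevent. Section 2.3 says "Symptomatic VTE has been reported in up to 4% of patients undergoing autologous reconstruction using abdominal flaps", without saying whether those patients had prophylaxis, and its other figure, "1 patient in 25 with a Caprini score >8 had a breakthrough VTE event", was observed despite daily enoxaparin. Neither is a risk without prophylaxis. The same section also quotes up to 20% asymptomatic VTE. Weighing all-grade bleeding against DVT or PE would moreover count a bruise as equal to an embolism. So the documents do not yield 4 points as an alternative margin.
- A reader might infer that the margin was fitted to the sample size, because 7.49 points is the smallest margin that 37 per arm supports at 80% power. That only inverts the formula in step 1; the documents do not say which figure came first.
- A reader might call the 17% to 45% false claims. A true rate of 3.96% lies inside the margin, so meeting it is correct by that standard. The figures show how permissive the standard is, not an error rate.
- A reader might describe the tolerated excess as 6.7 times the control rate. That multiple belongs to the total of 8.82%; the excess is 5.7 times.

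**Conclusion.** The point holds as a should-fix. The margin is unexplained, covers bleeding of any grade, and on the plan's own baseline accepts 8.82% against 1.32%. Meeting it would justify a statement about an absolute excess of 7.5 points, not a statement that bleeding is similar or that apixaban is as safe. The planned test and odds ratio do not address the margin.

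The boundary and its multiples follow directly from the plan's figures. The 6.7 rests on the assumed 1.32% and falls to 1.75 if the baseline is 10%. The 17% to 45% rest on confidence limits that I assumed, and the lower figure belongs to the interval recommended here. The documents do not show that the margin is clinically wrong, and I do not propose another.

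**What to change.** Change Sections 9.1, 11.1 and 11.4 in the same way, keeping 100 patients and the stated margin.

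1. Make the primary result the absolute difference in 90-day bleeding risk (apixaban minus enoxaparin), with a two-sided 95% score-type interval such as Newcombe, and compare its upper limit with 7.5 points. Keep the odds ratio as a secondary summary.
2. State beside the margin that it corresponds to 8.82% on apixaban against an assumed 1.32% on enoxaparin. Limit the conclusion to the absolute excess that the upper confidence limit excludes. State that bleeding will not be reported as similar, as safe, or non-inferior without that qualification.

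This costs protocol wording and no extra patients. The price is a narrower claim. The sponsor should also know that the stated 80% does not carry over to the Newcombe limit: under the plan's own rates the margin would be met in about 47% of trials at 50 per arm. That is a further reason to present the result as an estimate with its limits.

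### The 37 per arm for 80% power holds only at an unstated one-sided 5%; at the printed two-sided 5% the same formula gives 70%, and score or Newcombe limits give less than 80% at either level

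*Combined protocol and SAP*

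**What the plan says.** Section 11.1 (repeated in 9.1 and 11.4) sizes the trial "with 80% power to detect a non-inferiority margin of -0.075", "assuming a 1.32% baseline in bleeding events among patients dosed on daily enoxaparin" and a "1.73% rate of bleeding in direct oral anticoagulant (DOAC) arm patients over 90 days". From this, "our analysis expects enrollment size of 37 patients per arm". Enrolment is then raised for a "25% dropout rate over the course of the study, which results in a sample size of 100 (50 patients per arm").

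The formula is described only as standard. For the analysis, the same section says "Two-sided 5% significance levels will be used to identify statistically significant results", names an exact Pearson chi-squared test, and adds "The outcome will be reported as an odds ratio with 95% confidence intervals". The analysis is by intention to treat: "all randomized patients will be analyzed within the groups they were originally allocated to". No one-sided level, non-inferiority test or confidence limit for a risk difference appears anywhere.

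**The concern.** The sample size and the stated significance level do not seem to describe the same test. A non-inferiority conclusion from a 95% interval is a one-sided 2.5% test, and 37 per arm looked too small for 80% power at that level.

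The margin is also an absolute risk difference, while the planned outputs are a test of no difference and an odds ratio interval. Neither can show that a risk difference lies within 7.5 points. The margin carries a minus sign for a harmful outcome, and the plan does not say which arm is subtracted from which.

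The 80% is the stated justification for enrolling 100 patients. If it is not delivered, readers will underestimate the chance of an inconclusive result. If alpha and interval are left open, they can be chosen after the data are seen.

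**Working it through.** **Inputs (section 11.1).** Enoxaparin rate pC = 0.0132; DOAC rate pT = 0.0173; margin 0.075 in the adverse direction; power 80%; 1:1 allocation; 25% dropout.

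**Reproducing the plan's figure.** Formula: n = (z_α + z_β)² × [pC(1−pC) + pT(1−pT)] / [margin − (pT − pC)]².

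- Variance term: 0.0132×0.9868 + 0.0173×0.9827 = 0.03003.
- Distance to the margin: 0.075 − 0.0041 = 0.0709.
- One-sided 5%: (1.645 + 0.842)² × 0.03003 / 0.0709² = 36.93, so 37. This matches.
- Dropout: 37/0.75 = 49.3, so 50 per arm. This matches.

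**At the printed level.** With 1.96 in place of 1.645, n = 46.88, so 47.

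| Formula power | 37 per arm | 50 per arm |
|---|---|---|
| One-sided 5% (90% interval) | 80.1% | 89.4% |
| Two-sided 5% (95% interval) | 70.2% | 82.5% |

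**Is the formula reliable here?** Expected bleeds in total are 37 × 0.0305 = 1.13, or 50 × 0.0305 = 1.53. A normal approximation is poor with so few events. I therefore summed the two binomial distributions over all likely outcomes and counted those whose upper limit for apixaban minus enoxaparin falls below 7.5 points. Type I error was taken with the true difference at the margin (8.82% v 1.32%). Farrington-Manning score and Newcombe limits agree in every case.

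| Limit | Power, 37 | Power, 50 | Type I error, 37 | Type I error, 50 | Nominal |
|---|---|---|---|---|---|
| Score/Newcombe, 95% | 20.8% | 47.1% | 1.4% | 1.7% | 2.5% |
| Score/Newcombe, 90% | 55.4% | 60.1% | 4.3% | 3.7% | 5% |
| Wald, 95% | 65.7% | 79.0% | 7.9% | 6.1% | 2.5% |
| Wald, 90% | 86.7% | 80.8% | 15.3% | 7.5% | 5% |

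**Individual outcomes show why.**

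- No bleeds in either arm, 37 each (probability 0.9827³⁷ × 0.9868³⁷ = 0.32). The Newcombe upper limit is z²/(n + z²). At 95% this is 3.84/40.84 = 9.4 points, which fails. At 90% it is 2.71/39.71 = 6.8 points, which passes. The score statistic is 1.73, between 1.645 and 1.96. A Wald interval has zero width here and counts the outcome as a success.
- No bleeds in either arm, 50 each: the 95% limit is 3.84/53.84 = 7.1 points, which passes.
- One apixaban bleed against none, 50 each: limits of 10.5 points (95%) and 8.5 points (90%), which fail either way.

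Power moves in steps. With the 95% score or Newcombe limit it is 25% at 47 per arm and 48% at 48, so a single figure at one size would mislead.

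**The case against.** The arithmetic itself is sound: 37 and 50 both reproduce at one-sided 5%. The two-sided 5% sentence directly precedes the chi-squared test, so it may have been meant for a test of difference and not for the margin. That is a fair reading, but no other level is printed. If one-sided 5% was intended the plan must say so, and score or Newcombe power is still only 55% to 60%.

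If all 50 per arm are analysed, as intention to treat suggests, the plan's formula gives 82.5% even at two-sided 5%. That is correct, but the plan itself expects 25% dropout, and enumerated score or Newcombe power at 50 with a 95% interval is 47%.

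Other inputs can give 37 at one-sided 2.5%: setting both arms to 1.32% gives 36.35. That discards the stated 1.73%. Reversing the sign of the difference gives 38 and treats more bleeding as a benefit.

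The plan does not name a score or Newcombe limit, so the low power figures contradict no stated method. This stands: they illustrate a choice the plan leaves open, and another method would give other values. An Agresti-Caffo 95% limit, for instance, gives 53% at 37 and 60% at 50, with type I error of 3.4% against 2.5%.

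The type I errors above are for a 1.32% control rate. Over control rates from 0 to 20%, the score and Newcombe maxima at 37 per arm are slightly above nominal: 5.6% for the 90% limits and 2.6% to 2.7% for the 95% limits. The margin's sign matters less, since with both stated rates only an adverse 7.5-point margin gives 37 at one-sided 5%.

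**Conclusion.** The concern holds. With both stated rates taken in the adverse direction, 37 per arm gives 80% power only at one-sided 5%, which is printed nowhere. At the only printed level the formula gives 70% at 37 and needs 47.

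Under the plan's own rates, a limit that keeps its type I error within nominal at the 1.32% control rate gives 21% to 60% power, depending on the interval level and on whether 37 or 50 per arm are evaluable. Of the limits tabulated, only the 90% Wald limit reaches 80%, and it does so with type I error of 15.3% (37 per arm) or 7.5% (50 per arm) against 5%.

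The alpha conflict does not depend on the choice of interval; the enumerated powers do. All figures assume true rates of 1.32% and 1.73%. This must be corrected, because the 80% is the stated basis for the sample size and the primary margin has no decision rule.

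**What to change.** 1. State the alpha, interval method and direction. For example: non-inferiority is concluded if the upper limit of the two-sided 95% (or 90%) score or Newcombe interval for the bleeding risk difference, apixaban minus enoxaparin, is below +7.5 percentage points.
2. Replace the 80% with the power achieved under that choice at both 37 and 50 evaluable per arm. For score or Newcombe limits this is 21% and 47% (95% interval), or 55% and 60% (90% interval). If another method is chosen, recompute both power and type I error.
3. Present the primary result as an estimated risk difference with its confidence limit.
4. Make the same change in sections 9.1, 11.1 and 11.4.

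The cost is protocol wording in three places and a less favourable power statement. No extra enrolment is requested.
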